### 3.1.4 Determination of Sample Size

For this study, no prospective calculations of statistical power have been made. The sample size has been selected to provide information on safety, tolerability, PK, and efficacy following single doses of ATYR1923. There will be 30 patients randomized 1:1:1 to ATYR1923 1 mg/kg, 3 mg/kg, or placebo, respectively.

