#### 3.4.2 Secondary

- Time to hospital discharge,
- Time to recovery (WHO score  $\leq 3$ ),
- Proportion of patients achieving recovery by Day 14 and Day 28,
- Duration of supplemental oxygen ( $O_2$ ) requirement,
- Number of days with fever (temperature  $>100.4^{\circ}\text{F}$  [ $38.0^{\circ}\text{C}$ ]),
- Change from baseline in WHO Ordinal Scale score on Days 5, 7, 14, 28, and 60,
- Time to improvement from baseline based on at least a 1 point reduction in WHO Ordinal Scale score,
- All-cause mortality at Days 14, 28, and 60.

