### 4.9.2 Multiple Comparisons and Multiplicity

Given the exploratory nature of this study, all comparisons of treatment groups versus placebo will be interpreted in an exploratory manner and thus no adjustments for multiplicity will be performed. P-values provided are deemed to be exploratory.

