### 4.9.4 Key Secondary and Exploratory Efficacy Analyses

Secondary and exploratory endpoints will be analyzed according to the type of endpoint as described below. If data are sparse for any of the exploratory endpoints, summaries may be limited to descriptive statistics of available data or listings only as appropriate.

Time to event endpoints will be analyzed using Kaplan Meier method. The total number of patients with an event, the total number censored and Kaplan-Meier survival estimates with associated 95% CI (25% percentile, median, and 75% percentile) will be presented by treatment group. Further, crude proportions for having the event at timepoints with events observed (derived as: cumulative number of subjects with events / number of subjects in treatment group at baseline) along with 95% Wilson Score intervals with continuity correction will be provided.

Further, Kaplan-Meier estimates at 5, 6, 7, 10, 14 and 28 days from first study drug administration will be provided with associated 95% CI.

A survival plot will be produced with the probability of an event (0% to 100%) along the Y-axis and time in days along the X-axis.

The hazard ratio of ATYR1923 1 mg/kg versus Placebo, ATYR1923 3 mg/kg versus Placebo, and ATYR1923 Total versus Placebo with corresponding 95% CI and p-values will be estimated from a single Cox Proportional Hazards model.

All efficacy summaries and analyses will be based on mITT Set, unless otherwise stated.

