Days with fever up to Day 14 will be used as a sensitivity analysis. Days will be calculated the same as described for Days of supplemental oxygen (O2) up to Day 14.

Change from baseline in WHO Ordinal Scale score

The description of the WHO Ordinal Scale score is shown in [Section 6.2](#). The Number and percentage of patients on WHO Scale scores and change from baseline (-7, -6, -5, -4, -3, -1, 0, 1, 2, 3, 4) will be presented by visit. Shift table will be presented by visit as well.

Simple Ordinal logistic regression on the WHO Scale score at each visit (Days 5, 7, 14, 28, and 60) will be performed to compare ATYR1923 1 mg/kg versus Placebo and ATYR1923 3 mg/kg versus Placebo. Firth logistic regression ([Firth, 1993](#)) on the collapsed WHO Ordinal Scale (0-3 versus 4-8) at each visit (Days 5, 7, 14, 28, and 60) will be performed as well.

Distribution of WHO Ordinal Scale at 1, 2, 3, 4, 5, 6, 7, 10, 14, 28 and 60 days will be visualized by treatment group using an stacked bar chart. These figures will only consider scheduled assessments and in case the scheduled assessment is not available the mapped unscheduled TC follow up assessments as defined in [Section 4.2](#).

Time to Improvement in Clinical Status

Time to improvement in days is the time in which the patient sees a decrease after study treatment in the WHO Ordinal Scale score from baseline by at least 1 point, derived as:

date of decrease in WHO scale compared to baseline by at least 1 point - study drug administration date; or date of discharge from hospital - study drug administration date, whichever occurs first.

In the case that a patient has not decreased in the WHO scale or withdraws from the study, they will be censored at EOS date. Time to improvement will be analyzed using the Kaplan-Meier methods and Cox Proportional Hazards model as described in the above.

Repeat analysis above for improvement of WHO Ordinal Scale score by at least 2 points.

Additionally, time to improvement will be analyzed using an adapted derivation: date of decrease in WHO scale compared to baseline by at least 1 point - randomization date; or date of discharge from hospital - randomization date, whichever occurs first.

Related output will be noted as sensitivity analysis.

Time to improvement (by at least 1 and 2 points) will be analyzed based on mITT and EE Set. Sensitivity analysis for time to improvement will be analyzed based on mITT only.

*All-cause mortality*

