#### 4.9.4.2.1 Subgroup Secondary Efficacy Analyses

Subgroups:

- BMI (<30,  $\geq 30$ ) at Baseline;
- WHO Score at Baseline (<5,  $\geq 5$ );
- Concomitant Medication: Remdesivir (yes, no), see [Section 4.8](#),
- Concomitant Medication Dexamethasone (yes, no), see [Section 4.8](#).

Secondary Efficacy Analysis to be repeated by subgroups mentioned above are

- Time to Hospital Discharge and proportion of patients achieving recovery (WHO scale score  $\leq 3$ ) by Day 14 and by Day 28,
- Summary of WHO ordinal scale score by visit,
- Time to recovery (WHO scale score  $\leq 3$ ).

Subgroup analyses will be only produced if the categories contain at least 5 subjects.

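### No between-arm efficacy model names baseline WHO score as a covariate, so at 10 patients per arm a chance severity gap would pass unadjusted into the estimates

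*SAP*

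**What the plan says.** The secondary endpoint in SAP 3.4.2 is "Change from baseline in WHO Ordinal Scale score on Days 5, 7, 14, 28, and 60". SAP 4.9.4.1 gives it two inferential analyses:

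- "Simple Ordinal logistic regression on the WHO Scale score at each visit (Days 5, 7, 14, 28, and 60) will be performed", comparing each dose with placebo. The outcome is the visit score, and no covariate is named.
- A Firth logistic regression "on the collapsed WHO Ordinal Scale (0-3 versus 4-8) at each visit (Days 5, 7, 14, 28, and 60) will be performed as well". No covariate is named.

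For the time-to-event endpoints, SAP 4.9.4 says that the three hazard ratios against placebo "will be estimated from a single Cox Proportional Hazards model", again with no covariate or strata named. Protocol 6.1 describes permuted blocks without a stratification factor.

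Baseline WHO score is used elsewhere. It is in the baseline table (SAP 4.7). SAP 4.9.4.1 tabulates change from baseline and shifts by visit, and defines time to improvement against each patient's own baseline. SAP 4.9.4.2.1 lists "WHO Score at Baseline" (<5, >=5) as a subgroup for time to discharge, recovery and the WHO summary by visit, provided the categories hold at least 5 subjects.

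**The concern.** Recovery is a threshold (WHO 3 or below, or discharge) on the scale that is measured at baseline. On the SAP 6.2 scale, a patient entering at 5 must fall two levels to reach 3 and a patient entering at 4 must fall one. The Firth cut at 0-3 versus 4-8 depends on the starting level in the same way. If one arm of 10 happens to contain several more patients at 5 or above, the unadjusted hazard or odds ratio reflects that gap as well as any drug effect. In a small Phase 2 study read mainly through its estimates, this could make an inactive dose look promising or an active one look weak. The existing uses of baseline would show the gap but would not correct the comparison for it.

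**Working it through.** **Inputs from the documents.** "There will be 30 patients randomized 1:1:1 to ATYR1923 1 mg/kg, 3 mg/kg, or placebo, respectively" (SAP 3.1.4), so 30/3 = 10 per arm. The same section says "For this study, no prospective calculations of statistical power have been made", so there is no power figure to reproduce. No alpha is stated; two-sided 0.05 is assumed, in line with the 95% intervals.

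**Assumptions.** The share of patients entering at WHO >=5 is varied from 20% to 50%, with 35% in the simulations. The prognostic ratio of baseline <5 versus >=5 is set at 1, 2, 4 or 8. The treatment ratio is 1 (null) or 2.5. None of these is in the documents.

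**Step 1: chance of a gap.** Let X and Y be independent Binomial(10, p) counts of patients at WHO >=5 in two arms. P(|X - Y| >= 3) is the sum of P(X=i)P(Y=j) over |i - j| >= 3. For at least one active arm against placebo, it is the sum over i of P(Y=i){1 - P(|X - i| < 3)^2}.

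| p | One active arm vs placebo | At least one of two active arms |
|---|---|---|
| 20% | 16% | 27% |
| 30% | 22% | 36% |
| 40% | 25% | 41% |
| 50% | 26% | 43% |

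For the pooled comparison (20 vs 10), a gap of 20 percentage points or more has probability 36% at p = 40%.

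**Step 2: what a gap does when the drug has no effect.** Simulation, 10 vs 10, 4,000 trials per setting. The table gives median estimates where the active arm has exactly 3 fewer / 3 more severe patients. Ratios above 1 favour the active arm.

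| Model | Prognostic ratio | Unadjusted | Adjusted for <5 vs >=5 |
|---|---|---|---|
| Cox | 2 | 1.29 / 0.81 | 1.08 / 1.05 |
| Cox | 4 | 1.47 / 0.72 | 1.04 / 1.05 |
| Ordinal | 2 | 1.27 / 0.77 | 1.04 / 1.00 |
| Ordinal | 4 | 1.58 / 0.63 | 0.95 / 1.00 |

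Each cell rests on roughly 250-290 trials. A separate Cox run of 6,000 trials gave 1.25 / 0.82 unadjusted and 0.99 / 1.01 adjusted (ratio 2), and 1.48 / 0.68 and 0.98 / 1.04 (ratio 4).

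**Step 3: size of the tests over all randomisations.** Likelihood-ratio tests at nominal 5% rejected in 5.6-6.8% of null trials unadjusted and in 6.6-7.9% adjusted.

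**Step 4: power at a treatment ratio of 2.5, each test calibrated to a true 5% size.**

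| Prognostic ratio | Cox unadjusted to adjusted | Ordinal unadjusted to adjusted |
|---|---|---|
| 1 | 42% to 38% | 18% to 18% |
| 2 | 39% to 41% | 20% to 18% |
| 4 | 28% to 39% | 17% to 19% |
| 8 | 20% to 37% | 15% to 18% |

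Monte Carlo error on a figure near 40% is about 1.96 x sqrt(0.4 x 0.6/4000) = 1.5 points, so the 2-point changes are close to noise.

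**Step 5: context.** Schoenfeld power for 10 vs 10 with all 20 events is Phi(sqrt(20/4) x ln HR - 1.96). At HR 2 this is Phi(1.550 - 1.96) = 34%; at HR 2.5 it is Phi(2.049 - 1.96) = 54%. For 80% power the events needed are 4 x (1.96 + 0.8416)^2 / (ln HR)^2 = 66 and 38. The study has low power with or without adjustment.

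**The case against.** **Baseline is not ignored.** A reader might infer that the plan disregards baseline WHO score, or never analyses the change endpoint as change. The documents do not support this: change counts, shift tables, the improvement definition, the baseline table and the subgroup all use it. This stands. What remains is narrower. The tables are descriptive, the improvement definition sets the event and does not adjust the comparison, and the subgroup leaves out the WHO regressions and time to improvement and gives no combined adjusted estimate.

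**The SAP is silent, not explicit, for two models.** Simple supports a treatment-only ordinal model. For Firth and Cox the absence of covariates is inferred from their not being named. This also stands.

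**Randomisation protects the test.** Step 3 shows that the unadjusted test stays near its nominal size, so reading the plan as giving a biased or invalid test would be wrong. The error exists only given the imbalance that occurs, and the adjusted test is the more liberal of the two.

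**Power.** A reader might infer that the ordinal regression loses power. Step 4 does not support that: the calibrated change is about -2 to +3 points. The study claims no power, its primary endpoint is safety, and SAP 4.9.2 says "P-values provided are deemed to be exploratory".

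**Prognostic strength is assumed.** This stands. For time to improvement even the direction is unclear: going from 5 to 4 needs only a step down in oxygen support, while going from 4 to 3 means coming off oxygen.

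**Conclusion.** The point holds as a gap in the between-arm models. No efficacy model names a baseline severity covariate, and randomisation does not stratify by severity. A gap of 3 or more severe patients between an active arm and placebo has a chance of about 22-26% if 30-50% enter at WHO >=5. With no drug effect, a gap of 3 shifts the hazard ratio to about 1.3/0.8 or 1.5/0.7, and the odds ratio to about 1.3/0.8 or 1.6/0.6, for prognostic ratios of 2 and 4. Adjustment removes nearly all of the shift. The calibrated Cox power gain is about 2 to 11 points over the same range, and a loss of about 4 points if baseline is not prognostic. Apart from the 10 per arm, these figures rest on the assumed baseline mix and prognostic strength. The ordinal comparison also lacks the ATYR1923 Total contrast that the Cox model has; that is a separate minor point.

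**What to change.** Keep the specified unadjusted models as the main analyses. The revision history shows that SAP versions 2.0 and 3.0 contain post-unblinding changes, so putting adjusted models in their place now would be a model change made with the data exposed.

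Add baseline WHO score, at the SAP's own <5 vs >=5 split, as one covariate in the Cox, ordinal and Firth models. Present these as sensitivity analyses labelled post hoc, in keeping with SAP 3.2. Use penalised or permutation inference: the adjusted likelihood-ratio tests ran at 6.6-7.9%, so profile-likelihood intervals alone are not shown to be enough. Report adjusted and unadjusted estimates side by side next to the baseline WHO distribution by arm.

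Note in the report that the two can differ without any imbalance. In the 6,000-trial run with a true hazard ratio of 2.5 and prognostic ratio 4, trials with equal numbers of severe patients gave median estimates of 2.06 unadjusted and 2.66 adjusted. A difference between the two is therefore not by itself a measure of confounding.

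The cost is one extra model term and a few outputs, using data already collected. The downsides are slightly liberal tests and a small loss of power if baseline turns out not to be prognostic.

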#### 4.9.4.2 Exploratory Efficacy Analyses

Unless specified, standard descriptive statistics (mean, standard deviation, median, minimum, maximum) will be used to summarize continuous variables below. Number and percentage will be presented for categorical variable below. For the number of days, will count the actual days not considering discontinuation or death.

*Change from baseline in supplemental oxygen requirement at day 3, 5, 10, 14 and discharge*

Subject's status of supplemental oxygen requirement (none, low flow: face mask or nasal canula, high flow: high-flow oxygen or non-invasive ventilation) will be summarized at each scheduled visit. Shift to baseline table will be provided for each scheduled visit as well.

By-patient listings of all supplemental oxygen use including unscheduled assessments will be provided.

*Proportion of patients requiring intubation, and among those patients, number of days of intubation.*

Proportion of patients requiring intubation, and among those patients, number of days of intubation derived as:

date of extubating or EOS, whichever occurs first – date of intubation + 1, if intubation happened after study drug administration.

By-patient listings of all respiratory support including unscheduled assessments will be provided.

*Pharmacodynamics (PD) biomarkers and potential COVID-19 disease biomarkers*

See [Section 4.11.3](#).

#### 4.9.4.2.1 Subgroup Secondary Efficacy Analyses

Subgroups:

- BMI (<30,  $\geq 30$ ) at Baseline;
- WHO Score at Baseline (<5,  $\geq 5$ );
- Concomitant Medication: Remdesivir (yes, no), see [Section 4.8](#),
- Concomitant Medication Dexamethasone (yes, no), see [Section 4.8](#).

Secondary Efficacy Analysis to be repeated by subgroups mentioned above are

- Time to Hospital Discharge and proportion of patients achieving recovery (WHO scale score  $\leq 3$ ) by Day 14 and by Day 28,
- Summary of WHO ordinal scale score by visit,
- Time to recovery (WHO scale score  $\leq 3$ ).

Subgroup analyses will be only produced if the categories contain at least 5 subjects.

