7.1.6. Concomitant Medication and Other Restrictions During the Study

7.1.6.1. Prohibited or Restricted Concomitant Medications and Substances

The following treatments and procedures are prohibited prior to and/or during study participation, as indicated below:

- All investigational agents or devices (other than ATYR1923) within 3 months for small molecules and 6 months for biologics, or 5 half-lives (if known) of the agent, whichever is longer, before the first study drug dose and through the duration of study drug treatment.
- Use of chronic (>30 days) oral corticosteroids for a non-COVID-19-related condition in a dose higher than prednisone 10 mg or equivalent per day.
- Use of immunosuppressive medications/immunotherapy including but not limited to sarilumab and tocilizumab.
- Off-label use of commercially-available medications for the treatment of SARS-CoV-2.

All other concomitant medications and procedures (including remdesivir) are allowed.

Concomitant medications, including supplemental oxygen, are to be recorded in the source documents and in the eCRF.

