8.6.4. Concomitant Medications

Medications that are ongoing at Screening are to be documented. Furthermore, all medications and supplements, including supplemental oxygen, the patient receives during their course of hospitalization as part of their standard of care as well as during the study are to be documented in the source documents and in the eCRF.

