#### 4.8 Concomitant Medications and Procedures

Medications will be coded using Anatomical Therapeutic Chemical (ATC) Classification codes by WHO Drug Global version Mar 2019 Format C3. Prior and concomitant medications will be summarized by ATC class level II, and Preferred Term, using the Safety Set.

Medication start and stop dates will be compared to study drug administration date to allow medications to be classified as either prior only, both prior and concomitant, or concomitant only. Missing or partial start dates will be imputed as described in [Section 4.3](#).

Medications that start and stop prior to study drug administration will be classified as prior only. If a medication starts before study drug administration and stops on or after study drug administration or stop date is missing, then the medication will be classified as both prior and concomitant. Medications will be classified as concomitant only if they have a start date on or after study drug administration.

In the summary of prior and concomitant medications, each subject will be counted once within each unique term. For example, if a subject takes amoxycillin on 2 separate occasions, the subject is counted only once under the corresponding ATC class.

Summaries and by-subject listings will be given for Safety Set. The summary will group the medication by Prior only, Prior and Concomitant and Concomitant only.

Listings will include medication/therapy start and end date:time or ongoing status, dose, route, frequency, primary indication for the medication, AE term if applicable, medical history term if applicable and concomitant medication flag (Prior only, Prior and Concomitant, Concomitant only).

Additionally, number of patients taking Remdesivir (ATC Level 2 code “J05”) and/or Dexamethasone or other glucocorticosteroids (ATC Level 2 code “H02”) and/or Convalescent Plasma (ATC Level 2 code ‘J06) flagged as “Prior and Concomitant” or “Concomitant only” will be provided by treatment group for the Safety Analysis Set.

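### The remdesivir and dexamethasone subgroups count drugs first started after dosing, so membership partly depends on length of stay; a minor bias that is cheap to remove

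*SAP*

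**What the plan says.** SAP Section 4.9.4.2.1 lists four subgroups. Two are fixed at baseline: BMI, and the item beginning "WHO Score at Baseline (<5". The other two are "Concomitant Medication: Remdesivir (yes, no), see" Section 4.8, and "Concomitant Medication Dexamethasone (yes, no"), with the same cross-reference. Neither drug item mentions baseline or sets a time limit. The outcomes repeated by subgroup are time to hospital discharge, recovery by Day 14 and Day 28, WHO score by visit, and time to recovery. A subgroup analysis is produced only if its categories hold at least 5 subjects.

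Section 4.8 counts users of these drugs who are "flagged as “Prior and Concomitant” or “Concomitant only” will be provided by treatment group". It defines the second flag as follows: "Medications will be classified as concomitant only if they have a start date on or after study drug administration". For steroids, the count covers "Dexamethasone or other glucocorticosteroids" under class code H02.

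Protocol Section 8.6.4 records "all medications and supplements, including supplemental oxygen, the patient receives during their course of hospitalization" and during the study. Protocol Section 7.1.6.1 adds: "All other concomitant medications and procedures (including remdesivir) are allowed". Later starts are therefore both possible and captured.

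**The concern.** A subgroup variable should be settled before treatment can influence it. Here a patient first given remdesivir on Day 5 is a 'yes', while a similar patient discharged on Day 4 is a 'no'. Length of stay governs the opportunity to start an inpatient drug, and length of stay is one of the outcomes analysed.

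There are two consequences. First, 'yes' patients stay longer than 'no' patients by construction. Second, if ATYR1923 speeds discharge or changes how often these drugs are started, the two arms are sorted into 'yes' and 'no' differently. The subgroup HRs can then differ although the effect is the same in every patient. A reader who sets the two HRs side by side could conclude that ATYR1923 works better with, or without, background remdesivir or dexamethasone.

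**Working it through.** **Stated figures.** None can be reproduced: SAP Section 3.1.4 says that no power calculation was made, and the documents give no effect size, discharge rate or rate of drug starts. They do give 30 patients at 1:1:1, so 10 per arm, or 20 against 10 for ATYR1923 Total versus placebo.

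**Assumptions, none from the documents.**
- Exponential time to discharge, placebo median 6 days, censoring at Day 60.
- 50% or 80% on the drug before dosing.
- 30% or 60% of the others would start it within 14 days if still inpatient.
- Start rate on ATYR1923 equal to placebo, or halved.
- True discharge HR 1.0, 1.5 or 2.0, the same for every patient (above 1 means faster discharge).
- With or without a severity factor shared by discharge and drug starts.

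**Closed form, no severity factor.** Let λ0 and λ1 be the discharge rates on placebo and ATYR1923, and μ the start rate. A patient not on the drug at dosing stays a 'no' only if discharge comes before a start. Among such patients, time to discharge is exponential with rate λ + μ. With equal start rates:

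HR in 'no' = (λ1 + μ) / (λ0 + μ)

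- λ0 = ln 2 / 6 = 0.1155 per day. At true HR 1.5, λ1 = 0.1733.
- 60% starting by Day 14: μ = −ln(0.4)/14 = 0.0654.
- HR in 'no' = (0.1733 + 0.0654) / (0.1155 + 0.0654) = 0.2387/0.1809 = 1.32, although the true HR is 1.5.
- At true HR 2: (0.2310 + 0.0654)/0.1809 = 1.64.
- No effect on discharge, but μ halved on ATYR1923: (0.1155 + 0.0327)/0.1809 = 0.82, an apparent harm where there is none.

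**Simulation.** 300,000 patients per scenario, ATYR1923 Total versus placebo at 2:1, with a Cox model within each subgroup. At true HR 1.5 with 60% starting and no severity factor, the 'no' HR was 1.31-1.32, matching the closed form. Ranges below run over all assumed rates, with and without the severity factor.

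| Scenario | Yes/no ratio of HRs, SAP definition (truth 1.00) |
|---|---|
| No effect on discharge or on starts | 0.99-1.01 |
| True HR 1.5, equal start rates | 1.05-1.19 |
| True HR 2.0, equal start rates | 1.08-1.31 |
| No effect on discharge, starts halved on ATYR1923 | 1.10-1.25 |
| True HR 1.5 and starts halved | 1.15-1.42 |

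With membership fixed before dosing, the ratio is 0.98-1.02 in every scenario. An independent rerun gave the same pattern; individual ratios moved by a few hundredths, which is simulation error. The share of patients moved into 'yes' by a post-dose start was 2-20%.

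In the first row the HRs are not distorted, but median stay is 6.1-7.8 days in 'yes' against 3.0-5.0 days in 'no'. Under the pre-dose definition both are 5.6-6.0 days.

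**Bias against random error.** The variance of a log HR is roughly 1/d1 + 1/d0, with d1 and d0 the events per arm. In the most favourable case every patient is discharged and 'yes' and 'no' split evenly, giving 10 and 5 events in each subgroup. The variance of the log ratio of HRs is 2 × (1/10 + 1/5) = 0.60, so SD 0.77. A true ratio of 1 could then be observed anywhere between exp(−1.96 × 0.77) = 0.22 and exp(1.96 × 0.77) = 4.5. The bias on the log scale is ln 1.19 = 0.17 at HR 1.5 and ln 1.31 = 0.27 at HR 2, at most about a third of that SD.

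**The case against.** The strongest reply is that this hardly matters here. With 10 patients per arm and categories as small as 5, neither definition supports a reliable reading. SAP Section 4.9.2 declares the comparisons and p-values exploratory, and no interaction test is planned. All of this stands, and it limits the point to a minor one. It does not justify the definition: subgroup HRs will still be read side by side, and this bias does not shrink with more data.

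The size also depends on how many patients first start these drugs after dosing, which the documents do not say. If nearly all use began before dosing, the bias is small. That stands too.

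Two stronger readings are tempting. A reader might infer that the SAP definition produces a false interaction whatever ATYR1923 does. It does not: with no effect on discharge or on drug starts, the ratio stays at 0.99-1.01, and only the contrast between 'yes' and 'no' patients is distorted. A reader might also infer that the dexamethasone subgroup definitely takes in every glucocorticosteroid, including the chronic low-dose oral steroids that the protocol does not exclude. The documents leave this open. Section 4.9.4.2.1 names dexamethasone alone, the wider wording in Section 4.8 belongs to a count for the Safety Set, and Section 4.8 also summarises by preferred term, so dexamethasone can be separated.

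**Conclusion.** The point holds as a minor correction. The text lets post-dose starts define two subgroups, nothing elsewhere in either document restricts them, and the resulting bias has a known mechanism. A false difference between subgroups requires that ATYR1923 affects discharge or the starting of these drugs. Given that, and under the assumed rates, the ratio of HRs is off by about 5-19% at a true HR of 1.5, 8-31% at a true HR of 2, and 10-25% if only post-dose starts are halved. At this sample size, chance will usually outweigh it. The documents do not support calling it a threat to the trial's main conclusions: the primary endpoint is safety, and these subgroup analyses are exploratory.

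**What to change.** In SAP Section 4.9.4.2.1:

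- Define each drug subgroup by use started before the study drug infusion and ongoing at dosing. Count later starts as 'no'.
- Use start date and time, not the existing flag alone. Section 4.8 compares dates, so a drug begun on Day 1 hours before the infusion could be flagged as concomitant only and wrongly become a 'no'. The Section 4.8 listings already carry medication times.
- State a rule for Day 1 starts with no recorded time. Section 4.2 has a convention for untimed baseline assessments on the dosing date that could be adapted.
- Identify the drugs by preferred term (remdesivir; dexamethasone). If all of H02 is meant, relabel the second subgroup as systemic glucocorticosteroids.
- Label the revised subgroup analysis post hoc. The Revision History shows that versions 2.0 and 3.0 already contain post-unblinding changes, and Section 3.2 requires the label for analyses devised after database lock.

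No new table of post-dose starts is essential: the Section 4.8 summary of concomitant-only medications already largely reports them by arm.

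The cost is a few lines of SAP text and some reprogramming. The downside is fewer 'yes' patients, so a category may fall below the 5-subject minimum and that subgroup analysis would not be produced.
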